Version 2.0

Sponsored by:

Desmond Tutu HIV Foundation

The signature below constitutes the approval of this protocol and the attachments, and provides the necessary assurances that this study will be conducted according to all stipulations of the protocol, including all statements regarding confidentiality, and according to all applicable legal and regulatory requirements and regulations as well as ICH and SA GCP guidelines.

I, as the Principal Investigator, agree to conduct this study in full accordance with the provisions of this protocol. Publication of the results of this study will be governed by DTHF policies.

I have read and understand the information in this protocol and will ensure that all associates, colleagues, and employees assisting in the conduct of the study are informed about the obligations incurred by their contribution to the study.

Principal Investigator:

Signed:

Name:

Date:

Title:

PROTOCOL SUMMARY

Purpose:	To assess the Acceptability, safety and use of daily oral PrEP (FTC/TDF or Truvada®) in healthy, HIV-uninfected adolescents, 15-19 years of age
Primary objective	
1. To evaluate the Acceptability and Use of a daily regimen of oral PrEP (FTC/TDF), as a component of a comprehensive HIV prevention package [with HIV testing, STI management, risk reduction counseling, access to condoms, PEP, counseling and referral for male circumcision (for boys)], for adolescents between 15 and 19 years of age.2. To evaluate the safety of a daily regimen of oral PrEP (FTC/TDF), as a component of a comprehensive HIV prevention package [with HIV testing, STI management, risk reduction counseling, access to condoms, PEP, counseling and referral for male circumcision (for boys)], for adolescents between 15 and 19 years of age.

Secondary objective	
 1. To evaluate adherence to a daily regimen of oral PrEP (FTC/TDF), as a component of a comprehensive HIV prevention package for adolescents between 15 and 19 years of age. 2. To evaluate change in sexual activity, perceptions of sexual risk, risk compensation, and health behaviours, including condom use, in adolescents, between 15 and 19 years of age, who take a daily regimen of oral PrEP (FTC/TDF) over a 12 month period. 3. To assess study participants' and their partners' perceptions on key issues associated with oral PrEP (FTC/TDF), including adherence barriers, adherence facilitators, and general product knowledge, as part of a comprehensive HIV prevention package [with HIV testing, STI management, risk reduction counseling, access to condoms, PEP, counseling and referral for male circumcision(for boys)]. 4. To assess HIV incidence in study participants during the course of study participation
Exploratory objectives	
 1. To explore the utility of Dried Blood Spot (DBS) and the impact of biofeedback of results as an adherence enhancing strategy, among HIV-negative adolescents, between 15 and 19 years of age 2. To explore the relationship between daily PrEP usage and sexual practices and behavior in adolescents.

Design	
The study is designed as an open-label, single arm cohort study, to evaluate the Acceptability, safety and Use of daily oral PrEP (FTC/TDF) in 150 adolescents (approximately 75 participants at each site), ages 15-19 years, their adherence to study product, and any changes in their sexual and health behaviors over a 12-month (52 week) period. All participants will complete an initial (12 week) 3- month period, during which they will receive PrEP as part of a combination prevention package. At all subsequent visits, participants will be offered the opportunity to hear real-time feedback of drug level data as part of their adherence counseling or they may choose to have adherence counseling without the feedback of drug level data. The decision about feedback as well as self reported adherence will be captured via interviewer administered questionnaires at each follow up visit. At the first 3 month (week 12) visit and 3 monthly (weeks 24, 36, 48) intervals thereafter participants will be offered the following options: full package + PrEP, stop PrEP and continue with rest of package or alternatively re-start PrEP if previously stopped. This will occur during protocol-specified study visits.
 
Participants will be followed regardless of PrEP usage for a total of 12 months (52 weeks). PrEP may be stopped at any other clinic visit but recommencement can only occur at a scheduled visit when all medical criteria are met including a negative HIV test. Adherence counselling will be offered at every visit with options to have drug level feedback or not as part of this counselling.

Study site	The study will be conducted at The Desmond Tutu HIV Foundation research site in Masiphumelele, Cape Town and the Perinatal HIV Research Unit (PHRU) site in Soweto, near Johannesburg.
Study drugs	FTC/TDF or Truvada® is a 200mg/300mg fixed dose combination tablet containing emtricitabine (FTC) and tenofovir disoproxil fumarate (TDF).
Study population	Healthy, HIV-uninfected adolescents, 15 and 19 years of age
Number of participants	150 enrolled participants (approximately 75 participants at each site)

Treatment Regimen	Participants will be provided with a supply of FTC/TDF tablets, taken orally, once daily for first 3 months. Thereafter, these tablets will only be supplied to those who indicate willingness to take PrEP and who do not have a clinical contraindication to do so.
Study Duration	Participants will be scheduled to participate in the study for 12 months or 52 weeks. Accrual will require approximately 4 months (16 weeks).
Duration of participation	Each participant will be scheduled to receive study product for 52 weeks.
Primary endpoints	
Acceptability
 
 ○ The proportion of participants who report willingness to use the study regimen, take up PrEP and remain on PrEP as part of a comprehensive prevention package. ○ Assessment of acceptability as per questionnaire administered at study end. 
Use
 
 ○ Number of adolescents who continue to use PrEP after the initial 3 month period. ○ The total time on PrEP for each adolescent and for the cohort as a whole by self report. 
Safety
 
 ○ Grades 2, 3, and 4 clinical and laboratory adverse events;

Secondary endpoints	
Adherence:
 
Adherence to daily regimens of oral PrEP as evidenced by the use of self-report, pill counts, and proportion of participants on FTC/TDF who have detectable drug levels, in those participants who have indicated willingness to take PrEP and who have had tablets administered
 
 ○ Proportion of doses that are taken as instructed. ○ Proportion of blood samples with detectable drug levels ○ Proportion of adolescents with detectable drug levels who report using PrEP ○ Proportion of scheduled HIV testing appointments missed, in relation to individual characteristics (age, sex, number of partners, use of other prevention methods) and the characteristics of the product. 
Sexual Behavior
 
 ○ Reported number of steady and casual sex partners, condom use (and change after introduction of study product), substance use prior to or during sex, as evidenced by participant responses to interviewer-administered questionnaires and focus groups. 
HIV Incidence
 
HIV infection, as measured by seroconversion of study participants during the approximate 12 months (52 weeks) of follow-up.

---------------------	--

Exploratory endpoints	
Impact on adherence of drug (FTC/TDF) levels as measured in Dried Blood Spot/Plasma given as biofeedback
 
 ○ Number of counselling opportunities in which drug level feedback is requested vs total number of counseling events ○ Number and nature of participants who request drug level feedback. ○ Correlation between self reported adherence and drug levels at each visit for each participant ○ Correlation between self reported adherence and drug levels at each visit in the study overall. ○ Proportion and number of participants whose adherence to study product improves when receiving the results of DBS/Plasma compared to those who do not receive feedback of results as measured by endpoints above. 
Relationship between daily PrEP usage and sexual practices and behavior in adolescents
 
 ○ Sexual behavior data obtained using a questionnaire and focus group.
-----------------------	---

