The rationale for this study design is based on some of the feedback received from the VOICE and FEMPREP studies. Women in these studies reported high PrEP usage, remained in study and yet drug levels indicated very poor PrEP usage (Marazzo et al CROI 2013). Some rationale for this has been that PrEP acceptability was low, but with a keen perception among participants that study participation hinged on pill adherence. Thus, despite information that drug levels would be assessed, participants chose to report pill usage falsely. By making it very clear that trial participation does NOT hinge on PrEP usage (other than the first 3 months) we hope that we will get a more accurate assessment of real PrEP usage. We also hope that if participants really want to be taking PrEP, that adherence to product will persist. Other open label studies such as iPrEx OLE suggest this may be the case. By designing the study with an “opt out” arm we hope that we will create an authentic comparator group for participants taking oral PrEP (FTC/TDF) persistently and adherently, in order to assess any significant differences in adolescents taking oral PrEP (FTC/TDF) versus those who choose NOT to do so. We recognize that these may include demographic differences but may also include perceptions of risk, sexual activity, etc. In addition, we hope that this will give us a true sense of pill usage among this population- data that is currently unknown and required in order to more accurately model the impact of this intervention in this age group.

Both groups will be treated equally, except for administration of TDF/FTC therapy to those who select to include PrEP in their prevention package.

It was felt by the protocol team that the question of use and acceptability would best be answered by employing an open label design. The three month initial phase will mean that everyone will at least be exposed to 3 months of PrEP usage.

Adherence to medication can be measured in different ways depending on the condition and the

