7.4 FOLLOW UP VISITS (AFTER WEEK 13 AND UP TO WEEK 48; VISITS AT 24, 36, 48)

For the initial product usage lead-in period (Weeks 4-12), study participants will be asked to adhere to the study product. After the 12 week lead in period, participants will be asked at subsequent 12 weekly visits whether they wish to continue PrEP, stop PrEP or restart PrEP as part of their prevention package (Week 12, 24 and 36). All participants regardless of product usage will be followed for the duration of the study. Participants will be advised to make these decisions at scheduled study visits. Reasons for decision will be enquired upon and recorded in CRFs.

Participants will also however be told they can contact study site at any time and also when they should with-hold PrEP for medical reasons.

Participants will complete scheduled 4 weekly follow-up visits until week 12. Thereafter, all visits will be 12 weekly regardless of PrEP addition to the prevention package or not. Target dates are set based on the enrollment date, and do not change if subsequent actual visits take place before or after the target date.

As it will not always be possible to complete follow-up visits on the targeted dates, follow-up visits may be completed within an approximate 2-week window around the target date (-/+7days from the target date).

The following procedures will be completed at each Follow-Up Visit (wks 24, 36, 48):

- Administrative/Behavioural Procedures
 - Locator information (update)
 - At all visits
 - HIV pre-and post-test counseling, including risk reduction counselling
 - At all visits
 - Social harms and/or benefits
 - At all visits
 - Sexual risk behavior questionnaire

- At all visits
- Provision of condoms
 - At all visits
- Provision of study drug (for participants who choose to receive study product)
 - at visits Wk 12, 24, 36 .
- Acceptability assessment
 - at visits Wk 12, 24, 36, 48.
- Adherence Counselling (if participant is on study product)
 - at visits Wk 12, 24, 36, 48 (week 48 visit will be feedback on last 3 months only since no more product will be offered).
- Feedback of plasma drug level/DBS results (to participants on study product who agree to receive this information at the time of adherence counseling.)
 - At visits Wk 12, 24, 36, 48.
- Adherence assessment (including pill counts) and counselling (for participants who choose to receive study product)
 - At visits Wk 12, 24, 36, 48

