- Study drug supplies and instructions/counseling (for participants who choose to receive study product)
 - At all visits where study product is administered week 12, 24, 36
- Reimbursement
 - At all visits
- Schedule next visit
 - At all scheduled visits, except Final Study Visit
- Clinical Procedures
 - Contraceptive counselling and provision as appropriate
 - At all visits
 - Physical exam
 - At week 48
 - As clinically indicated
 - Update medical and menstrual history and/or current medications if applicable

- At all visits
- Record/update adverse events (AEs) applicable
 - At all visits
- Laboratory Procedures
 - HIV rapid testing
 - At all visits
 - As clinically indicated at unscheduled visits (reported exposures)
 - STI testing
 - Herpes (HSV-2),
 - Chlamydia, and Gonorrhea testing (0, 12, and 48 weeks)
 - Urine dip stick testing
 - Every 12, 24, 36, 48 weeks
 - Aspartate aminotransferase/alanine aminotransferase (AST/ALT) testing
 - Every 12, 24, 36, 48 weeks
 - Serum chemistries, including creatinine, glucose, electrolytes, and lipase
 - Every 12, 24, 36, 48 weeks
 - Full Blood Count testing
 - Every 12, 24, 36, 48 weeks
 - Urine pregnancy testing (for females)
 - At all visits
 - Contraceptive counseling
 - At all visits
 - Measurement of study drug levels by Plasma/DBS
 - At 12, 24, 36, 48 weeks.

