7.8 LABORATORY EVALUATIONS AND PROCEDURES

Laboratory evaluations will include the following:

- Hepatitis B surface antigen and antibody testing
 - At Screening
- Urine pregnancy test
 - At every visit
- HIV serology
 - At every visit
- HSV-2 serology
 - At screening, Week 12, 48
- Chlamydia, and Gonorrhea.

- At screening, Week 12, 48
- Serum chemistries, creatinine only
 - Week 52
- AST, ALT
 - Screening, Week 12, 24, 36, 48 and 52
- Full Blood Count
 - Screening, Week 12, 24, 36, 48
- Haematocrit
 - Week 4, 8, 52
- DBS / Plasma drug level sampling
 - Week 4, 8, 12, 24,
 - Week 36, 48, for those who remain on study product
 - Week 52, Plasma only for those who remain on study product
- Urine dip stick
 - Screening, Week 12, 24, 36, 48

The location of laboratory evaluations will depend on laboratory capacity.

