Urine pregnancy testing		X	X	X	X	X	X	X	X	X
Urine dip stick testing		X			X	X	X	X	X	
Adherence counseling				X	X	X	X	X		
* IF clinically indicated, per local standard X = Mandatory # = on PrEP										

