CHAMPS: Choices For Adolescent Prevention Methods for SOUTH AFRICA

Pilot study B: “PlusPills”

A Demonstration Open Label Study to Assess the Acceptability and Use of Truvada Pre-exposure Prophylaxis in Healthy, HIV-Uninfected Adolescents, 15-19 Years of Age.

STATISTICAL ANALYSIS PLAN

OVERVIEW AND SUMMARY OF DESIGN

The study is designed as an open-label phase 2 demonstration project, to evaluate the acceptability, safety, feasibility, as well as the adherence to daily oral PrEP (FTC/TDF) for HIV-1 prevention, among 150 male and female adolescent participants at two sites (with approximately 75 participants at each site), ranging in ages between 15 and 19 years old, over a 12 month period. The study will also investigate the uptake and utility of feedback to the participants real time about drug levels obtained from dried blood spots/plasma during adherence counselling.

STUDY ENDPOINTS

Primary Acceptability/Use Endpoints:

Consistent with the primary study objective to evaluate the acceptability and use of daily oral PrEP (FTC/TDF) in HIV-negative adolescents, ages 15-19 years, the following primary safety endpoints will be assessed:

- The proportion of participants who report willingness to use the study regimen, take up PrEP and remain on PrEP as part of a comprehensive prevention package.
- An acceptability questionnaire will be administered at the final study visit to assess the delivery of PrEP and the content of the study visits, including the user-friendliness of the medication regimen (including an assessment of side effects), the delivery format, the dosing strategy, and the clinic visit schedule.
- Number of adolescents recruited, enrolled, and retained in the study.

Primary Safety Endpoint:

CHAMPS: Choices For Adolescent Prevention Methods for SOUTH AFRICA

Pilot study B: “PlusPills”

A Demonstration Open Label Study to Assess the Acceptability and Use of Truvada Pre-exposure Prophylaxis in Healthy, HIV-Uninfected Adolescents, 15-19 Years of Age.

- Grades 2, 3, and 4 clinical and laboratory adverse events;

Secondary Endpoints:

Consistent with the secondary study objectives to evaluate the adherence and sexual behaviour of daily oral PrEP (FTC/TDF) in HIV-negative adolescents, ages 15-19 years, the following endpoint will be assessed:

Adherence Endpoint:

- Adherence to daily regimens of oral PrEP as evidenced by self-report, pill counts, and proportion of participants assigned to FTC/TDF who have detectable drug levels.

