A Demonstration Open Label Study to Assess the Acceptability and Use of Truvada Pre-exposure Prophylaxis in Healthy, HIV-Uninfected Adolescents, 15-19 Years of Age.

sum tests, replaced by analysis of variance or u-tests for global comparisons across polytomous groupings.

3. Primary: Safety

Grades 2, 3, and 4 clinical and laboratory adverse events

Analysis:

This analysis will be based on descriptive statistics.

B. Secondary Endpoints:

1. Secondary: Adherence

Adherence to daily regimens of oral PrEP as evidenced by the use self-report, pill counts, and proportion of participants on FTC/TDF who have detectable drug levels.

Proportion of doses that are taken as instructed.

Proportion of blood samples with detectable drug levels

Proportion of adolescents with detectable drug levels who report using PrEP

Analysis Plan:

There are 3 different measures of PrEP adherence that will be used for the primary adherence endpoint: Participant self-report, pill count results, and detectable drug levels.

While the distributions of each of these measures may vary, a priori we anticipate that analysis of each of these 3 measures will use two different binary metrics from data at each study visit: (i) perfect adherence (defined as adherence data that do not suggest any missed doses, e.g., pill count data consistent with daily dosing, or no missed doses detected on self-report); and, (ii) effective adherence (defined as adherence levels that are consistent with protection against HIV exposure based on available data from PrEP efficacy trials, e.g., >85% doses taken, from pill count, or self-report; or therapeutic drug levels on biological assays).

Note that drug levels will be used in analyses of effective adherence only.

Analyses of adherence data will be based on the binary constructs of perfect and effective adherence as well as continuous measures of the proportion of PrEP doses taken; both the

CHAMPS: Choices For Adolescent Prevention Methods for SOUTH AFRICA

Pilot study B: “PlusPills”

A Demonstration Open Label Study to Assess the Acceptability and Use of Truvada Pre-exposure Prophylaxis in Healthy, HIV-Uninfected Adolescents, 15-19 Years of Age.

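### After week 12 adherence is measured only in current PrEP users, so the by-visit and pooled figures can shift through opt-out alone, and the week-24 drug-level denominator is inconsistent

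*Protocol*

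**What the plan says.** **Who is in the adherence endpoint.** The Protocol Summary gives the population as those "in those participants who have indicated willingness to take PrEP and who have had tablets administered". The adherence part of the SAP's data analysis plan (and Protocol 10.6) uses the "proportion of participants on FTC/TDF who have detectable drug levels". The SAP endpoint list (and Protocol 10.2) has the "proportion of participants assigned to FTC/TDF who have detectable drug levels", although nobody is assigned in a single-arm study with opt-out.

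**Who is assessed.** Section 7.4 schedules "Adherence assessment (including pill counts) and counselling (for participants who choose to receive study product" at weeks 12, 24, 36 and 48.

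**Who gives a drug-level sample.**
- Section 7.3: all participants at weeks 4, 8 and 12.
- Section 7.4: "At 12, 24, 36, 48 weeks", with no qualifier for any of the four visits.
- Section 7.8: week 24 is grouped with weeks 4, 8 and 12 without restriction. The limit starts later: "Week 36, 48, for those who remain on study product".
- Table 1: weeks 24 to 52 carry the # mark, and the footnote reads "X = Mandatory # = on PrEP".
- Section 7.6: participants who stop product keep all procedures except product supply and drug levels.

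**How it is reported.** Protocol 10.6 and the SAP analyse adherence at each visit and aggregated over the study, for the whole cohort and for subgroups. One listed measure is the share of blood samples in which drug is detected.

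**Use.** Section 4.2 bases continued use and time on PrEP on DBS or plasma levels. The Protocol Summary bases time on PrEP on self-report. The analysis text in 10.6 and the SAP counts any self-reported use as remaining on PrEP, whatever the adherence.

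**The concern.** The Protocol Summary wording does not itself say current users. That reading comes from the data collection rules: after week 12 someone who has opted out has no pill count, no adherence assessment and, under Table 1 and section 7.6, no drug level. The denominator is then self-selected and can change at each quarterly choice.

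Two things follow. First, a visit-to-visit change in adherence mixes behaviour with membership of the group, and the pooled figure mixes lead-in visits that sample everyone with later visits that do not. Second, if section 7.8 is followed, opted-out participants would be sampled at week 24 but not at week 36, and that switch alone could move the blood-sample proportion.

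Section 2.5 hopes that the design "this will give us a true sense of pill usage among this population", because such data are needed to model impact in this age group. That purpose calls for drug-confirmed use over everyone enrolled, beside the figure among users. A spurious rise would also point the same way as the section 2.5 hypothesis that counselling with drug-level feedback enhances adherence.

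**Working it through.** **Starting denominator.** The plan gives no adherence or opt-out rate, so it has no figure of its own on this point to reproduce. The enrolment target does reproduce: 135/(1 − 0.10) = 150.

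**Inputs.** N = 150 (SAP). The remaining inputs are assumptions: a = share adherent at week 12; oA and oN = opt-out rates among adherent and non-adherent users. For simplicity, adherent means drug detected, non-adherent and opted-out participants have none detected, all opt-out happens at week 12, nobody restarts or is lost, and no individual changes behaviour.

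**Formulas.**
- Adherence among current users = a(1 − oA) / [a(1 − oA) + (1 − a)(1 − oN)]
- Drug-detectable share of all enrolled = a(1 − oA)

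**Worked case: a = 60%, oA = 10%, oN = 50%.**
- Week 12: 90 adherent and 60 not, so 60%.
- Remaining: 90 × 0.90 = 81 adherent and 60 × 0.50 = 30 not, so 111 users.
- Among users: 81/111 = 73.0%, a rise of 13.0 points.
- Among all enrolled: 81/150 = 54.0%, a fall of 6.0 points.

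**Range** (adherence among users, change from week 12 in points):

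| oA / oN | a = 40% | a = 60% | a = 80% |
|---|---|---|---|
| 5% / 20% | 44.2 (+4.2) | 64.0 (+4.0) | 82.6 (+2.6) |
| 10% / 30% | 46.2 (+6.2) | 65.9 (+5.9) | 83.7 (+3.7) |
| 10% / 50% | 54.5 (+14.5) | 73.0 (+13.0) | 87.8 (+7.8) |
| 20% / 60% | 57.1 (+17.1) | 75.0 (+15.0) | 88.9 (+8.9) |
| 20% / 20% | 40.0 (0) | 60.0 (0) | 80.0 (0) |
| 30% / 10% | 34.1 (−5.9) | 53.8 (−6.2) | 75.7 (−4.3) |

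In the first four rows user-only adherence rises by 2.6 to 17.1 points. The all-enrolled share falls by a × oA, from 0.40 × 5% = 2 points to 0.80 × 20% = 16 points. These are four chosen pairs, not bounds. Pairing 5% with 60% at a = 40% gives 0.38/(0.38 + 0.24) = 61.3%, a rise of 21.3 points.

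**Week 24 (worked case).** If only users are sampled, 73.0% of samples have drug detected; if everyone is sampled, 54.0%. The gap is 19.0 points. Following section 7.8 literally, the figure would go from 54.0% at week 24 to 73.0% at week 36 with nothing changed.

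**Pooled figure (worked case, weeks 4 to 48, with 60% also taken for weeks 4 and 8).** Detected samples: 3 × 90 + 3 × 81 = 513 under every rule.
- Users only from week 24: 513/(450 + 333) = 513/783 = 65.5%.
- Week 24 unrestricted: 513/(450 + 150 + 222) = 513/822 = 62.4%.
- All enrolled at every visit: 513/900 = 57.0%.

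**The case against.** **Conditioning on users is deliberate.** Section 2.6.7 separates uptake, persistence and quality of adherence and sets out to study all three. Doses taken and pill counts mean nothing for someone with no tablets. This stands: the user-only figure is legitimate and should stay.

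**The cohort is not ignored.** A reader might infer that the plan gives no adherence information for the enrolled cohort. The documents do not support that. Everyone is sampled at weeks 4, 8 and 12; section 4.2 lists a drug-level count of continuing users and cohort time on PrEP; persistence is analysed by product-limit methods, with an analysis treating those lost to follow-up as non-adherent. The gap is narrower. The analysis text falls back on self-report, the loss-to-follow-up analysis does not address voluntary opt-out, and the reference to the cohort overall sets it against subgroups without saying how an opted-out participant counts.

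**The plan makes no coverage claim.** A reader might also infer that it overstates coverage in the cohort. It nowhere presents user-only adherence as coverage, so that reading fails too.

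**The week-24 conflict is limited.** Section 7.4 is unqualified and does not say that everyone is sampled. Section 7.6 agrees with Table 1, which leaves the grouping in section 7.8 as the passage in conflict. The participant-level endpoint is restricted to those on FTC/TDF whoever is bled; the exposed measure is the proportion of blood samples. This conflict is separate from the opt-out effect and does not cause it.

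**Little hangs on it formally.** Adherence is secondary and largely descriptive, with modelling labelled exploratory. That limits the harm but does not make a by-visit trend interpretable.

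**Conclusion.** The point holds in this form: after week 12, adherence by visit and pooled over the study describes a changing, self-selected group, and the plan does not state the denominator. Under the assumed pairs in which less adherent users leave more often, the user-only figure rises by about 3 to 17 points with no change in behaviour. Size and direction depend wholly on opt-out rates that the documents do not give: there is no shift if opt-out is unrelated to adherence, and a fall if adherent users leave more. Restarts are allowed and are not in the calculation.

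The week-24 sampling passages contradict each other. In the worked case that moves the week-24 blood-sample proportion by 19 points and the pooled one by about 3 (65.5% against 62.4%). The drug-level Use endpoint in section 4.2 has no matching analysis, so drug-confirmed use over all enrolled is not carried through after the lead-in.

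It does not follow that the user-only trend should be replaced by an all-enrolled one. That would mix attendance and the mandated stops of section 9.7 (pregnancy, toxicity, HIV infection) with adherence. The two figures answer different questions and belong side by side.

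**What to change.** 1. Reconcile sections 7.4, 7.6, 7.8 and Table 1 into one week-24 sampling rule, and use the same wording in each place.
2. In the SAP, state the denominator of every adherence measure at every visit, including whether being on PrEP refers to the interval just ended or to the choice made that day. Replace the reference to assignment.
3. Keep adherence among current users. Beside it, report the number and proportion of all enrolled with detectable drug, counting opt-outs as not using. Show missed visits and protocol-mandated stops as separate categories, and add a sensitivity analysis that counts missed visits as not covered. This also supplies an analysis for the drug-level Use count in section 4.2.
4. Add a note to the tables that the user-only trend and the pooled figure reflect a group whose membership changes.

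The cost is one extra table column and a less favourable cohort-level figure. The added column needs no further blood draws, because opt-outs are classified by rule.
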